1. OBJECTIVES

1.1 Primary Aims

- 1.1.1 To recruit 72 former smokers at high risk of developing lung cancer who will be randomly assigned to either receiving Avmacol® or placebo tablets for 12 months. Bronchoscopy-guided bronchial biopsy and brushing, bronchoalveolar lavage, nasal brushing, blood and urine samples will be collected from each subject at pre- and post-intervention time points.
- 1.1.2 To determine if daily oral dose of 120 micromole sulforaphane (SF) for 12 months can modulate the changes of bronchial dysplasia index, cell proliferation marker Ki-67, and apoptosis markers caspase-3 and TUNEL in bronchial biopsies in former smokers at high risk for lung cancer.

1.2 Secondary Aims

- 1.2.1 To explore if daily oral dose of 120 micromole SF for 12 months can modulate the changes of the lung cancer-related gene expression markers in bronchial epithelia in former smokers at high risk for lung cancer.
- 1.2.2 To explore if daily oral dose of 120 micromole SF for 12 months can modulate the changes of bronchial premalignant lesions-related gene expression markers in former smokers at high risk for lung cancer.
- 1.2.3 To explore if daily oral dose of 120 micromole SF for 12 months can modulate the similar changes of the gene expression markers in nasal epithelia as in the bronchial epithelia identified in Aims 1.2.1 and 1.2.2.

- 1.1.4 To determine the safety and toxicity of daily oral dose of 120 micromole SF for 12 months in former smokers at high risk for lung cancer.

2. BACKGROUND

2.1 Rationale for sulforaphane as a chemopreventive agent for lung cancer

Lung cancer is leading cause of lung cancer death in both men and women worldwide (1.5 million deaths) and in the US (158,000 deaths) (2,3). Cigarette smoking causes 90% of lung cancer (4). Smoking cessation is an obvious and practical strategy for lung cancer prevention for smokers. The smoking cessation programs and antismoking campaign have resulted in significant reduction in prevalence of cigarette smoking in the US, from 60% in late 1960s to 17% in 2015; currently there are more former smokers than current smokers (5). However, former smokers remain at high risk of lung cancer even after they quit smoking for many years (6). In fact, the majority of new lung cancer cases occur among former smokers (7,8). Unfortunately the preventive intervention for lung cancer targeting former smokers is lacking.

Epidemiological studies have shown that intake of isothiocyanates (ITCs), natural products formed from glucosinolates found in certain cruciferous vegetables such as broccoli and its seeds, are associated with a reduced risk of lung cancer. Using a validated biomarker approach (9,10), we, for the first time, demonstrated that high urinary total ITCs, including both sulforaphane (SF) and phenethyl isothiocyanate (PEITC), were associated significantly with a 35% reduced risk of lung cancer (11). These novel findings stimulated many epidemiological and experimental studies on the potential lung cancer protection of dietary ITCs and cruciferous vegetables in many populations. A meta-analysis including 14 studies and more than 8,000 lung cancer cases reported a statistically significant 20% reduced risk of lung cancer for subjects with high intake of cruciferous vegetables (12). These data implicate a protective role of ITCs or cruciferous vegetables as a whole against the development of lung cancer in humans. However, epidemiological studies are inherent with measurement errors and potential confounding, thus the observed association between ITCs and lung cancer risk may not be causal. Furthermore, results from observational studies usually do not provide a biological underpinning.

Preclinical data in rodent models is quite persuasive for prevention of lung cancer with ITCs. In an experiment by Hecht *et al.* (13), 160 rats were assigned to 4 groups: 1) 60 rats treated by tobacco-specific lung carcinogen NNK (2 ppm) only, 2) 60 rats of NNK (2 ppm) plus PEITC (3 micromole/g diet), 3) 20 rats of PEITC (3 micromole/g diet) only, and 4) 20 rats untreated as controls. PEITC was added to diet at a non-toxic concentration for the entire study period (112 weeks) whereas NNK was added to the drinking water one week after the initial administration of PEITC. At the end of the study (after 112 weeks of PEITC and 111 weeks of NNK treatment), 70% of the NNK-treated only rats developed lung adenoma and adenocarcinoma while only 5% of rats treated with PEITC and NNK developed lung tumors, similar to those in the PEITC-treated only or untreated control rats. These results showed that PEITC, treated concurrently with NNK, a setting analogous to the situation of current smokers who are continuously exposed to tobacco carcinogens including NNK, completely inhibited carcinogen-induced lung tumors in rats.

In another experiment by Chung and colleagues (14) with a different study design, mice were treated with a mixture of tobacco carcinogens: 3 micromole benzo(a)pyrene [B(a)P] and 3 micromole NNK, given gavage once a week for 8 weeks first, stopped carcinogen treatment for 12 weeks, and then fed a diet containing different concentrations of sulforaphane (SF) (1.5 or 3.0 micromole/g diet) or phenethyl isothiocyanate (PEITC) (1.5 or 3.0 μ mole/g diet), for 22 more weeks. At the end of the study, the incidence of lung adenocarcinoma was reduced by a statistically significant 52% in mice treated with carcinogens plus SF, and by 55% in mice treated with carcinogens plus PEITC, compared with mice treated with carcinogens only. The tumor multiplicity was reduced by 70% in mice treated with carcinogens plus SF and by 60% in mice treated with carcinogens plus PEITC. These results show that both dietary SF and PEITC can inhibit the development of lung tumors induced by two major tobacco lung carcinogens – B(a)P and NNK. More importantly, the

chemopreventive agents SF and PEITC were given 12 weeks after the carcinogen treatment was stopped, a setting analogous to a situation of exposure for former smokers.

Besides the inhibition of tumor incidence and multiplicity, both SF and PEITC can inhibit cellular proliferation markers such as Ki-67 and induction of apoptosis (15), hallmarks of tumorigenesis. In the experiment by Chung and colleagues (14), dietary intake of SF (1.5 micromole/g diet) reduced number of lung cells expressing proliferative cell nuclear antigen, an alternative to Ki-67, by 61% (from 44.4 ± 1.9 to 17.3 ± 11.7) (14). In a double-blinded randomized clinical trial, women with abnormal mammograms and scheduled for breast biopsy who consumed SF precursor GR supplement (estimated daily urinary excretion of 9.7 μ mole total metabolites of SF) for 2-8 weeks showed significantly reduced Ki-67 labeling indices (LI) in breast benign tissue (16). Dietary SF and PEITC also induced markers of apoptosis in lung tissue of mice after treated with tobacco carcinogens. Compared with control animals, mice given SF (1.5 micromole/g diet) showed a statistically significant 6-fold increase (from 4.7 ± 1.9 to $29.3 \pm 4.7\%$) in activated caspase-3, and a 2-fold increase (from 12.7 ± 3.0 to $29.4 \pm 5.8\%$) in TUNEL (terminal transferase dUTP nick end labelling) of lung cells (14).

We recently completed two randomized, double-blinded, placebo-controlled clinical trials. The first trial was led by [name] to evaluate whether intake of SF enhances the detoxification metabolism of environmental carcinogens and toxicants such as benzene and acrolein in 283 subjects (89% were non-smokers) who were exposed to substantial levels of airborne pollutants in China. Intake of a broccoli sprout-derived beverage providing daily doses of 600 micromole GR and 40 micromole SF for 12 weeks significantly increased the urinary excretion of the detoxification mercapturic acids formed from benzene, an environmental carcinogen present in both tobacco smoke and polluted air, by 61% ($P < 0.001$) and acrolein by 23% ($P = 0.01$) (17). The median levels of the 24-hour urinary excretion of SF metabolites with this dosing regimen were 54-62 micromole across the intervention period (17). The second trial was led by [name] to evaluate if intake of PEITC inhibits the metabolic activation of tobacco-specific carcinogen NNK and enhances the detoxification metabolism of tobacco-nonspecific carcinogens and toxicants such as benzene and acrolein. Overall, intake of PEITC 40 mg/day for 5 days significantly inhibited NNK metabolic activation by 8% ($P = 0.023$), and increased urinary detoxification mercapturic acids formed from benzene by 25% ($P = 0.002$) and acrolein by 15% ($P = 0.005$), in 82 current smokers in the US. The mean level of the 24-hour urinary excretion of PEITC-NAC was approximately 80 micromole. These very similar results of the two trials on the detoxification of environmental carcinogens and toxicants suggest that both SF and PEITC have a very similar biological mechanism and share the strongly overlapping chemopreventive properties, as shown in the animal experiment (14).

These two randomized phase 2 clinical trials provided crucial data on the safe and effective dose and duration of treatment. The unbiased results of these trials elucidate the modulating effect of these ITCs on the metabolisms of tobacco-specific (NNK) and nonspecific carcinogens (benzene) and toxicants (acrolein) through specific

biological pathways. These encouraging results are very important for further development of these ITCs as primary chemopreventive agents against the development of lung cancer. However, these results are systemic and related to actions at the upstream on the lung carcinogenesis pathway. Before we can launch primary chemoprevention studies against the development of lung cancer as an end point, we need to demonstrate if ITCs such as SF can modulate the changes of downstream biomarkers on the lung carcinogenesis pathway such as bronchial dysplasia, cell proliferation and apoptosis, and gene expression in bronchial biopsies that have been shown to be directly linked to the development of lung cancer (18).

We propose to further evaluate the chemopreventive effect of SF against lung carcinogenesis through a randomized, double-blinded, placebo-controlled phase 2 clinical trial, a proof-of-principle study, with a longer treatment period (12 months) for former smokers who are at high risk for lung cancer. We hypothesize that intake of SF will improve pathological features of bronchial dysplasia, decrease cell proliferation and increase apoptosis in endobronchial biopsies, and improve the gene expression profile of lung cancer-related genes in endobronchial epithelial cells, all of which have been shown to predict lung cancer development and diagnosis (18,19). Successful outcome of this systemic analysis is crucial to further develop SF as a chemopreventive agent for the primary prevention of lung cancer. Our ultimate goal is to validate the efficacy of this readily available, widely accessible, inexpensive, natural compound as a primary chemopreventive agent against the development of lung cancer in humans.

Findings from epidemiological and animal experimental studies as well as from short-term randomized phase 2 clinical trials have shown cancer chemoprotective properties of sulforaphane. Although these results are encouraging, they are not sufficient and justifiable for launching large randomized phase 3 clinical trials to evaluate the efficacy of SF on reduction of lung cancer incidence and mortality as the primary endpoints, which require large amounts of resources and many years of intervention and many more years of post-intervention follow-up. We, the research community, have learned hard lessons from failed large placebo-controlled phase 3 chemoprevention trials when their premises were primarily based on the observed inverse association from epidemiological studies, but not by strong biological mechanisms supported by pre-clinical studies in animals and early phase randomized clinical trials in humans. These previously failed trials included CARET (beta-carotene and retinol) and ATBC (beta-carotene and alpha-tocopherol) (20,21). Therefore, direct evidence of a protective effect of SF on bronchial cellular and molecular biomarkers proposed here is crucial for further development of SF as a primary chemoprevention agent against the development of lung cancer in humans. The proposed study, if it proves our hypotheses to be true, will have significant public health implications on reduction of lung cancer incidence and mortality in former smokers.

2.2 Prior chemoprevention studies

There have been a limited number of phase 2 chemoprevention studies in lung cancer. Among them were the Iloprost and Celecoxib trials. We participated in the multicenter double-blind, randomized, placebo-controlled phase 2 trial of oral iloprost, a prostacyclin analogue, in current and former smokers with sputum cytological atypia or endobronchial dysplasia (22). Bronchoscopy was performed at study entry and after completion of the six-months treatment. Within each subject, we calculated the average histological score of all biopsies, the worst biopsy score, and the dysplasia index. Compared with former smokers in the placebo group, former smokers treated with oral iloprost exhibited a significantly greater improvement in average score (0.41 units better, $P = 0.010$), in the worst biopsy score (1.10 units better, $P = 0.002$), and in the dysplasia index (-12.5%, 95% CI -21.0% to -3.9%, $P = 0.006$). The 6-month treatment with iloprost did not show any improvement of histological scores in current smokers (22). Endobronchial dysplasia is a presumed precursor of non-small cell lung cancer (NSCLC). In a follow-up study of a high-risk cohort of subjects with endoscopic biopsies, persistence of bronchial dysplasia was associated significantly with a 7-fold increased risk of developing NSCLC (adjusted hazard ratio = 7.8, 95% CI 1.6-39.4). Furthermore, elevated Ki-67 LI at baseline endobronchial biopsies were associated significantly with increased bronchial dysplasia score, which predates the development of lung cancer (18).

Another similar phase 2 clinical trial was the celecoxib trial conducted by Mao and colleagues (23). The study enrolled former smokers (age ≥ 45 years, ≥ 30 pack-years of smoking, ≥ 1 year of sustained abstinence from smoking) to evaluate the impact of COX-2 selective inhibitor celecoxib on cellular and molecular events associated with lung cancer pathogenesis. The primary endpoint was bronchial Ki-67 LI after 6 month treatment. Celecoxib significantly reduced Ki-67 LI by an average of 34% ($P = 0.04$). Furthermore the decrease in Ki-67 LI correlated with a reduction and/or resolution of lung nodules on CT ($P = 0.008$).

Although both iloprost and celecoxib have shown effective on the reduced regression of bronchial dysplasia in former smokers (22-24), both are not available for further development as potential chemopreventive agents due to their toxicity (celecoxib) or lack of readily deliverable form such as tablets (ilo prost). Sulforaphane is a promising chemopreventive agent, a natural compound with minimal side effects, readily available, widely accessible, and inexpensive for mass production. Smaller trials with intermediate endpoints in high-risk subjects are needed to provide crucial data for further development of SF as a primary chemoprevention agent against the development of lung cancer in humans. The proposed study, if it proves our hypotheses to be true, will have significant public health implications on reduction of lung cancer incidence and mortality in former smokers.

3. PATIENT SELECTION

Seventy-two volunteers will be recruited for this phase II clinical trial.

3.1 Eligibility Criteria

- 1) Man or woman 55-74 years of age.
- 2) Patients with normal endobronchial biopsy findings or pre-cancerous lesions at baseline will be eligible for the study. Pre-cancerous lesions include (a) reserve cell hyperplasia, (b) squamous metaplasia, (c) mild dysplasia, (d) moderate dysplasia, and (e) severe dysplasia.
- 2) A former smoker who has a history of smoking with ≥ 30 pack-years, quits smoking within the past 10 years, and has more than 1 year sustained abstinence from smoking.
- 3) Female subjects must be of non-child bearing potential or must have a negative urine pregnancy test at screening (within 72 hours of first dose of study medication) if of childbearing potential.
- 4) Male and female subjects of childbearing potential must be willing to use adequate barrier methods of contraception from the time starting with the screening visit through 30 days after the last dose of study therapy.
- 5) Abstinence is acceptable if this is the established and preferred contraception for the subject.
- 6) Generally healthy with liver enzyme and blood count values within the ranges shown below on the blood sample drawn at the baseline screening visit.
Specifically:

White blood cells	$\geq 3,000/\text{mL}$
Total bilirubin	$\leq 1.5 \times \text{ULN}$ (upper limits of normal)
AST (SGOT)/ALT (SGPT)	$\leq 2.5 \times \text{ULN}$
BUN and serum creatinine	$\leq 1.5 \times \text{ULN}$
- 7) The presence of airflow obstruction on spirometry (GOLD 1-4 & $\text{FEV1}/\text{FVC} < 0.7$ & $\text{FEV1} < 0.8$) COPD; and/or any emphysema on CT scan.
- 8) Participants must have a Southwest Oncology Group (SWOG) performance status of 0-2 (Appendix 10).
- 9) Participants must be able and willing to undergo a bronchoscopy before and after treatment for 12 months.
- 10) Patients must be fully informed of the investigational nature of this study and must sign an informed consent in accordance with institutional and regulatory guidelines.

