Trace	22	663	2.58 (1.43-4.66)
Mild	37	493	5.04 (2.94-8.62)
Moderate/severe	16	315	3.20 (1.65-6.23)
P for trend			<0.0001

* Adjusted for age, sex, years of cigarette smoking, and number of cigarettes per day.

The presence of mild, moderate or severe radiographic emphysema on the LDCT scans at baseline was significantly associated with a 3- to 5-fold increased risk of developing lung cancer compared to smokers without emphysema (61).

We will recruit subjects for the present study from the existing PluSS participants who had mild, moderate or severe emphysema or GOLD II-IV COPD. Among the original PluSS participants who, as of 12/31/2015, were <75 years old, alive, free of cancer, and had quit smoking within the past 15 years, 356 had GOLD II-IV COPD (with or without emphysema), and additional 167 with mild, moderate or severe emphysema (without COPD). All these 523 subjects are potentially eligible for the proposed study. Based on our previous experience in the Iloprost study (22), which used a very similar protocol as the one proposed here, there was a 20% recruitment rate. Thus, we expect to fulfill our recruitment goal of at least 72 former smokers into the study within the first 3 years of the proposed study. With a 20% dropout rate based on our previous experience (22), we expect to have 60 study subjects who will complete the entire course of the trial.

If the proposed chemopreventive agent is effective, it will bring beneficial effect for study participants on reducing their risk of lung cancer. After the end of the study, all study participants can conduct their oral intake of Avmacol® since this dietary supplement is relatively cheap and commercially available.

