9. STATISTICAL AND SAMPLE SIZE CONSIDERATIONS

This is a randomized, double blind, placebo-controlled study to evaluate the efficacy of SF as a chemopreventive agent. Eligible subjects are former smokers with ≥ 30 pack-years smoking history who quit smoking < 15 years, and are considered at high risk for developing lung cancer. The proposed duration of therapy will be 12 months for each subject. The primary objective of this trial is to assess whether oral SF supplementation elicits an increased histologic response when compared to placebo in this population over a 12-month treatment period. The planned sample size is 72 subjects (36 per treatment arm). A block randomization scheme will be used to ensure that both treatment and placebo group have the same proportion of men and women, respectively. The randomization will be done at the UPMC Hillman Cancer Center.

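### The quit-smoking window and emphysema rule in Section 3.1 differ from those used to count the recruitment pool in Section 4.2 (and the window from Section 9), so the 523 people behind the accrual claim are not the population that 3.1 admits

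*Combined protocol and SAP*

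**What the plan says.** Section 3.1 (Eligibility Criteria) takes former smokers aged 55-74 with at least 30 pack-years, where the person "quits smoking within the past 10 years, and has more than 1 year sustained abstinence from smoking". Its lung criterion begins "The presence of airflow obstruction on spirometry (GOLD 1-4", joins this by ampersands to FEV1/FVC below 0.7 and FEV1 below 0.8, and offers as an and/or alternative "any emphysema on CT scan".

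Section 4.2 sets out a different group. Recruitment is to come from "existing PluSS participants who had mild, moderate or severe emphysema or GOLD II-IV COPD". The count, dated 12/31/2015, takes cohort members under 75, alive and cancer-free who "had quit smoking within the past 15 years, 356 had GOLD II-IV COPD", and adds 167 with mild-or-worse emphysema and no COPD. The total of 523 is described as potentially eligible in full. A 20% recruitment rate from the iloprost trial is then cited to support enrolling at least 72 within three years.

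Section 9 describes eligible subjects as former smokers with at least 30 pack-years "who quit smoking < 15 years, and are considered at high risk for developing lung cancer". It gives no GOLD or emphysema criterion.

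Section 3.3 says recruitment is mainly, not solely, from the Pittsburgh cohort, and that interested people may also telephone.

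**The concern.** Someone who quit 12 years ago is ineligible under 3.1, eligible under Section 9, and counted in 4.2. Someone with trace emphysema only can meet 3.1 but is outside the group that 4.2 counts. All of this is current text.

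Two things are at stake. First, staff working from the 4.2 list or from Section 9 could enrol people who breach 3.1, and the eligibility and statistical sections give different descriptions of the population analysed. Second, the feasibility statement multiplies a recruitment rate by a count made under rules other than the entry rules, so it does not show that the trial as specified can reach its target.

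**Working it through.** **Inputs.** From Section 4.2: 356 and 167 people, a 20% recruitment rate, and a target of at least 72 in three years. From Sections 3.1, 4.2 and 9: quit windows of 10, 15 and 15 years. From Table 2: emphysema counts for the whole cohort.

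**The plan's own figure.** 356 + 167 = 523, and 523 x 0.20 = 104.6, or about 105 recruits. The feasibility claim follows from its stated inputs.

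**Break-even.** 72 / 0.20 = 360 people, and 360 / 523 = 68.8%. The claim survives at a 20% rate unless the net loss from the pool exceeds 523 - 360 = 163 people (31.2%).

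**Effect of the 10-year limit alone.** The documents give no distribution of quit times, so the share of the 523 who meet the limit is an assumption. People = 523 x share; recruits = people x 0.20.

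| Assumed share within the limit | People | Recruits | Short of 360 by |
|---|---|---|---|
| 80% | 418.4 | 83.7 | none |
| 70% | 366.1 | 73.2 | none |
| 10/15 = 66.7% (even over 0-15 years, years 0-10 kept) | 348.7 | 69.7 | 11.3 |
| 9/14 = 64.3% (even over 1-15 years, years 1-10 kept) | 336.2 | 67.2 | 23.8 |
| 9/15 = 60.0% (even over 0-15 years, years 1-10 kept) | 313.8 | 62.8 | 46.2 |
| 50% | 261.5 | 52.3 | 98.5 |

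The three even-spread rows give 314 to 349 people and 63 to 70 recruits, just under the target. A modest lean towards recent quitting puts the figure back above 72.

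**Effect of the wider emphysema rule.** Table 2 lists trace emphysema separately: 22 + 663 = 685 people, against 37 + 493 + 16 + 315 = 861 with mild or worse. These counts are not restricted by age, quit time or COPD, so they support an illustration only. Suppose trace-only people without COPD stand to the 167 as 685 stands to 861. That adds 167 x 685/861 = 133 people, for a pool of 656. The three even-spread shares then give 437, 422 and 394 people, or 87, 84 and 79 recruits, all above 72.

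**Other mismatches.** As described, the 4.2 count applies no lower age limit, no pack-year minimum and no minimum abstinence. It is dated about a year and a half before funding began (6/14/2017, Section 13). Over that time some people pass the quit or age limit, while others may newly quit: 60% of the cohort smoked at enrolment.

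**The GOLD wording.** Section 3.1 names GOLD 1-4 but also requires FEV1 below 0.8. Section 4.2 groups FEV1 below 80% with GOLD II or higher. Read literally, 3.1 may admit few or no GOLD 1 patients by spirometry, so the criterion is unclear on its own terms.

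**Link to the sample size.** Section 9.1 sets 60 completers for 80% power and adds a dropout allowance to reach 72 (60 x 1.2 = 72). Neither 523 nor the quit window enters.

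**The case against.** The strongest reply is that this is a wording inconsistency with no demonstrated consequence. Section 3.1 is the itemised entry list; 4.2 is rationale and the Section 9 sentence is a summary, so a site would be expected to follow 3.1. The 105 expected recruits leave considerable slack over 72. The 10-year limit narrows the pool, but the emphysema rule widens it, the cohort is not closed to new quitters, and callers from outside it are accepted.

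Most of this stands as a limit on the conclusion. A reader might infer that the sample size of 72 falls with the 523, that recruitment will miss its target, or that power will drop below the stated level. The documents support none of these. The sample size is derived without the pool. A shortfall depends on an unreported quit-time distribution and on ignoring every offset. A power loss would further require the trial to stop short, whereas Section 9.1 says at least 72 will be randomised. A reader might also take GOLD 1-4 against GOLD II-IV as a clear population difference, but the FEV1 condition in 3.1 may remove most of it.

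The reply does not rescue the statement that all 523 are potentially eligible, nor the conflict over the quit window between the eligibility and statistical sections.

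**Conclusion.** The contradiction is established from the text: 10 years in 3.1 against 15 years in 4.2 and 9, and any emphysema in 3.1 against mild or worse in 4.2. Section 9 conflicts on the quit window only. The accrual support of 105 recruits therefore belongs to a population other than the one 3.1 admits.

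The size of the effect on recruitment is unknown. The fixed reference point is 360 eligible people, which assumes that the 20% rate carries over. The even-spread figures rest on that assumption and on applying the quit limit without any offset; they show that the question is close enough to need a recount, not that the target fails. The GOLD and FEV1 wording is an ambiguity within 3.1 to be resolved alongside.

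**What to change.** Use one quit window in Sections 3.1, 4.2 and 9, and one COPD/emphysema rule in 3.1 and 4.2, including how the GOLD grade and the FEV1 condition combine. Which rule to keep is for the sponsor to decide. Then recount the pool under all the agreed criteria, including age, pack-years and abstinence, at the start of enrolment. Replace 523 and the accrual statement with the new count and its product with the 20% rate, and compare the count with 360. If it is below 360, state that recruitment beyond the listed pool is needed and where it will come from.

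The cost is one wording amendment and one database query. The expected-accrual figure may become less favourable.
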